10.0 EFFICACY ANALYSIS

All proportions will be calculated using the FAS population for questions with an answer. The number of missing assessments will be included, but not part of the calculation. All efficacy analyses will be conducted using the FAS population, unless specified below.

10.1 Primary Efficacy Analysis

The primary endpoint is the time (in minutes) needed to prepare Alluzience and powder BoNT-A according to protocol. CCI

[figure not shown]

10.1.1 Sensitivity Analysis

The primary efficacy analysis will be repeated on the Per-Protocol population.

10.2 Secondary Efficacy Analysis

All secondary endpoints will be analyzed by treatment group using n and percentages for each proportion. The proportion of answers to each question will be presented by visit and treatment.

[figure not shown]
CCI

Sponsor: Galderma

[figure not shown]
Protocol Name: STAR

Plan Version: 1.0

CCI

CCI

[figure not shown]

Sponsor: Galderma

Protocol Name: STAR

Plan Version: 1.0

CCI

11.0 STATISTICAL/ANALYTICAL ISSUES

11.1 Handling of Dropouts or Missing Data

The number of missing values will be summarized and reported as appropriate. Missing values in the primary efficacy analysis will not be imputed. Sensitivity analyses using imputed data will be performed on statistical tests included in the secondary efficacy analyses (described in Section 10.2.9).

11.2 Multiple Comparisons/Multiplicity

No adjustments for multiple comparisons or multiplicity will be made.

11.4 Interim Analysis and Data Monitoring

No interim analysis will be performed.

12.0 SAFETY ANALYSIS

All safety data will be summarized descriptively based on the safety population. All of the safety analyses will be done using Observed Case (OC).

12.1 Glabellar Lines Treatment Administration

The Glabellar Lines Treatment Administration will be presented in a table and in a data listing. The listing will include the treatment date, investigator ID, needle size, if the injection was performed according to the protocol and a description of the treatment procedure if the injection was not performed according to the protocol. Product complaints will also be presented in a data listing.

12.2 Adverse Events

According to ICH E2A, an adverse event (AE) is any untoward medical occurrence in a patient or a clinical investigation subject administered a pharmaceutical product, and which does not necessarily have a causal relationship with this treatment. An AE can therefore be any unfavorable and unintended sign (including an abnormal laboratory finding), symptom, or disease temporally associated with the use of a medicinal (investigational) product, whether or not related to the medicinal (investigational) product.

Thus, any new sign, symptom or disease, or any clinically significant worsening of an existing sign, symptom or disease (including new episodes of a chronic disease [e.g., hay fever, allergy]) compared to the condition at the first visit, should be considered an AE.

Adverse events will be summarized by treatment group using the safety population. All AEs will be coded using MedDRA version 24.1 or later and presented by MedDRA SOC and PT in alphabetic order for SOC and by descending number in the SOC group and alphabetic order if the percentages are equal for PTs within an SOC. An AE with an onset date on or after the start of dosing in the active treatment period will be considered a treatment-emergent adverse event (TEAE).

While every effort will be made to obtain complete information on every reported AE, the following imputation rules will be followed for any respective missing AE data:

CCI

CCI

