#### 7.2.1.1.5 *Adverse Event (AE) Reporting Period*

The clinical study period during which AEs must be reported is the period from when the subject is treated with study product to the end of the subject's participation.

The Sponsor should be informed if the Investigator becomes aware of any unusual safety information or any safety information that appears to be drug-related involving a subject who has participated in a clinical study, even after a subject has completed the clinical study.

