#### **9.1.2.2      *Safety Analysis***

Adverse Events (AE) will be summarized by number of subjects and number of events per treatment group. Aes will be summarized by causality, system organ class , preferred term and maximum intensity. All related Aes will also be summarized by time to onset, duration and action taken.

Aes occurring before treatment will only be provided in subject data listings.

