3.2 Study Design

This is an open-label, randomized, interventional, two-armed, multi-centre study to investigate subject treatment perception and Investigator treatment experience when using Alluzience or vacuum-dried BoNT-A (powder BoNT-A) for treatment of GL. Subjects randomized to be treated with powder BoNT-A will only be followed for 1 month (Visit 3) while subjects treated with Alluzience will be followed for 6 months (Visit 6).

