12.2.1 Overview of Adverse Events

An overview summary table of AEs will be presented by treatment including the number and percentage of subjects reporting an AE for the following categories:

- Subjects reporting at least one AE
- Subjects reporting at least one treatment-related AE
- Subjects reporting at least one serious AE (SAE)
- Subjects reporting at least one treatment-related serious AE (SAE)
- Subjects reporting at least one AE leading to discontinuation of study
- Subjects with AE resulting in death on study

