12.2.2 Overview of Treatment-Emergent Adverse Events

A TEAE is an event that emerges during or after treatment, having been absent pre-treatment, or worsens relative to the pre-treatment state.

The number of events and the number and percentage of subjects by treatment with the following categories of TEAEs will be summarized by SOC and PT:

- Subjects reporting at least one TEAE by SOC and PT.
- Subjects reporting at least one TEAE by SOC, PT, and maximum intensity.
- Subjects reporting at least one TEAE by SOC, PT, and relationship (related/not related) to study drug.
- Subjects reporting at least one TEAE leading to discontinuation of study drug dosing by SOC and PT.
- Subjects reporting at least one serious TEAE by SOC and PT.

The number and percentage of subjects who experienced at least one TEAE will be summarized overall and for each SOC and each PT. The percentage will be based on the number of subjects in the safety population. Each subject will contribute at most one count per summarization category. In other words, if a

subject has more than one TEAE with same PT, the subject will be counted only once for that PT. Similarly, if a subject has more than one TEAE for a SOC, the subject will be counted only once in that SOC and PT.

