12.2.3 Relationship to Study Drug

A two-point scale (Yes/No) shall be used for the causality assessment. The Investigator shall be asked to indicate a response to each of the following questions in the eCRF:

- "Do you consider that there is a reasonable possibility that the event may have been caused by the study product?"
- "Do you consider that there is a reasonable possibility that the event may have been caused by the study product injection procedure?"

If the answer is "Yes" to either of these questions, the AE is considered related.

Summaries of related AEs (including the total number of events, number and percentage of subjects) will be displayed by treatment group according to the following:

- All AEs related to study product or injection procedure by SOC, PT, and maximum intensity (mild, moderate, or severe)
- All AEs related to study product or injection procedure by SOC, PT, and duration of event
- All AEs related to study product or injection procedure by SOC, PT, and number of days to onset of event
- All AEs by SOC, PT, and action taken (none, medical treatment, non-pharmacological treatment, subject withdrawn)
- All AEs unrelated to study product or injection procedure by SOC, PT, and maximum intensity (mild, moderate, or severe)

If a subject has multiple occurrences of the same SOC or PT, then only the related event will be summarized in the tables for that SOC and PT. Missing relationships will be considered related.

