Appendix A: Table 1 – Schedule of Assessments

1 month = 4 weeks/28 days Visit windows are calculated from Baseline/Visit 2 if not otherwise specified.	Visit 1 Group 1 and 2	Visit 2 Group 1 and 2	Visit 3/ Group 1 EoS Group 2	Visit 4 Group 1	Visit 5 Group 1	Visit 6/ET EoS Group 1
	Screening ¹	Treatment / Baseline ¹ (within 3 weeks after screening)	1-Month Follow-up (±7 days)	3-Month Follow-up (±7 days)	5-Month Follow-up (±7 days)	6-Month Follow-up (±7 days)
Informed Consent	X	(X) ²				
Demographic Data including, medical history & con-current diseases, previous facial treatments/ procedures	X	(X) ²				
Inclusion /Exclusion Criteria	X	X				
Adverse Events ³		X	X	X	X	X
Concomitant Medication/ Procedures	X	X	X	X	X	X
Urine Pregnancy Test ⁴	X	X				
Photography		X	X	X		X
Randomization		X				
Treatment		X				
End of study ⁵			X Group 2, powder BoNT-A			X Group 1, Alluzience
Investigator Assessments						
Reconstitution/Preparation Questionnaire		X				
Investigator Treatment Session Questionnaire ⁶		X				

CCI

1. Screening and treatment/baseline visits can be performed at the same day
2. Only to be conducted if no screening visit has been performed. Changes to medical history should be asked for if the screening and baseline visits are not performed on the same day.
3. AEs are collected from treatment to the end of the subject's participation.
4. Only for women of childbearing potential
5. Subjects in the powder BoNT-A treatment group will be followed 1 month and subjects in the Alluzience treatment group will be followed for 6 months.
6. Only for Alluzience-treated subjects
7. Only to be completed once for each Treating Investigator, per study product, after all enrolled subjects have completed Visit 2.
8. Performed pre-treatment

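### By-arm adverse event tables set about 168 days of Alluzience follow-up beside about 28 days of powder follow-up, with no common window in the readable plan

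*SAP*

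**What the plan says.** SAP 3.2 and 4.1 give the arms different follow-up: powder BoNT-A subjects leave at Visit 3 (Month 1) and Alluzience subjects at Visit 6 (Month 6). The schedule of assessments (Protocol Table 2, SAP Appendix A) counts a month as 28 days.

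AE collection follows each subject's own participation. Protocol 7.2.1.1.5 says that the "clinical study period during which AEs must be reported is the period from when the subject is treated with study product" until the end of participation. Note 3 of SAP Appendix A agrees: "AEs are collected from treatment to the end of the subject's participation".

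The tables are then laid out by arm:

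- SAP 12.2: "Adverse events will be summarized by treatment group using the safety population".
- SAP 12.2.1: "An overview summary table of AEs will be presented by treatment including the number and percentage of subjects reporting an AE", with rows for related AEs, SAEs, discontinuations and deaths.
- SAP 12.2.2: TEAEs by SOC and PT, with event counts. "The percentage will be based on the number of subjects in the safety population".
- SAP 12.2.3: related AEs by intensity, duration and days to onset, and unrelated AEs by intensity only.
- Protocol 9.1.2.2: AEs "will be summarized by number of subjects and number of events per treatment group".

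The TEAE rule in SAP 12.2 gives a start point but no end day. It mentions an active treatment period that the readable text does not define.

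**The concern.** Each percentage divides subjects with an AE by a head count, so it depends on how long those subjects were watched. Background events unconnected with treatment, such as colds, have six times as long to accumulate on Alluzience. The side-by-side columns can therefore make Alluzience look worse than powder when the underlying risk is the same. The all-cause, SAE, discontinuation and unrelated-event tables are most exposed, because none has a visible onset split. Related AEs are less affected, since they are also tabulated by days to onset.

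The by-arm concomitant medication and procedure tables (SAP 12.3 and 7.4) share the unequal follow-up. The medication table counts anything taken on or after dosing, whenever it was started.

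**Working it through.** **Inputs.** One month is 28 days (SAP Appendix A). Follow-up is 1 month on powder and 6 months on Alluzience (SAP 3.2), each final visit ±7 days. Planned group sizes are 50 and 100 (SAP 3.4). The plan states no AE rate or ratio, so there is no figure to reproduce. The risks below are assumptions, set equal in both arms.

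**Follow-up.** Powder 1 × 28 = 28 days; Alluzience 6 × 28 = 168 days; 168/28 = 6. For a constant background, expected events per subject differ 6-fold. Raw event counts differ (100 × 168)/(50 × 28) = 16,800/1,400 = 12-fold.

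**Subjects with at least one AE.** With acute risk *a* from the injection and background risk *b* per month:

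- powder: 1 − (1 − a)(1 − b)
- Alluzience: 1 − (1 − a)(1 − b)^6

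| a | b | Powder | Alluzience | Ratio |
|---|---|---|---|---|
| 0 | 1% | 1.0% | 5.9% | 5.85 |
| 0 | 5% | 5.0% | 26.5% | 5.30 |
| 0 | 20% | 20.0% | 73.8% | 3.69 |
| 10% | 2% | 11.8% | 20.3% | 1.72 |
| 20% | 2% | 21.6% | 29.1% | 1.35 |
| 10% | 0 | 10.0% | 10.0% | 1.00 |

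The largest value shown is not a ceiling. With a constant hazard, the ratio tends to 6.0 as risk becomes small. At the visit-window extremes that limit is 161/35 = 4.6 or 175/21 = 8.3.

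**With a Month 1 onset cut.** Both arms become 1 − (1 − a)(1 − b), so the expected ratio is 1.0 in every row. At b = 2%, a further 1 − 0.98^5 = 9.6% of Alluzience subjects would have an event in the separate post-cut table.

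**With events per subject-month instead.** Powder is a + b; Alluzience is (a + 6b)/6.

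| a | b | Powder | Alluzience | Ratio |
|---|---|---|---|---|
| 10% | 2% | 0.12 | 0.037 | 0.31 |
| 20% | 2% | 0.22 | 0.053 | 0.24 |
| 10% | 0 | 0.10 | 0.017 | 0.17 |

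Exposure adjustment reverses the distortion whenever AEs cluster early.

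**The case against.** The strongest reply is that no between-arm safety comparison is planned. The safety objective (SAP 3.1.4) covers Alluzience alone, safety is descriptive (SAP 12.0), and Protocol 9.1.4 excludes inference. The difference in follow-up is stated openly in both documents and will be reported alongside the tables. SAP 12.2.5 adds by-subject listings of deaths, SAEs and discontinuations, and SAP 4.2 and 14.2 put study days in listings. Much of this stands and limits the weight of the point. It does not correct the summary tables: the plan chose parallel columns, which invite comparison, and Protocol 11.8 aims at a public registry and a journal.

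The missing text is also a fair objection. SAP 4.0 is redacted, as is the passage after the imputation sentence in SAP 12.2, and the mock-ups are not available. A convention or footnote could sit there. The gap in 12.2 is introduced as imputation rules, so a window there is unlikely but cannot be excluded. The readable rows of the SAP 16.0 change log list no departure from Protocol 9.1.2.2. That is weak support, because the SAP adds AE tables beyond 9.1.2.2 without logging them.

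Finally, the ratios rest on assumed rates. Protocol 1.4 names headache and injection site reactions as the most frequent Alluzience reactions. If such early events dominate, the mixed rows (1.35 to 1.72) are nearer the mark than 5.85.

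**Conclusion.** The concern holds. As far as the plan can be read, the by-arm AE tables compare windows that differ six-fold, with no common cut and no caveat. Under equal assumed risk, the examples give crude ratios from 1.0 to 5.9, depending on how early AEs fall. The size in this trial cannot be predicted from the documents. The consequence is a misleading descriptive display, not a failure of the Alluzience safety objective, so the change is advisable but at the lower end of that grade. Confidence is medium because of the redacted text and the unavailable mock-ups.

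**What to change.** In SAP 12.2:

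1. Add by-arm AE and TEAE tables limited to events with onset on or before the subject's own Month 1 visit, or discontinuation if earlier. For a subject who misses Visit 3 but continues, cut at 28 days after treatment, which is Relative Study Day 29 under SAP 4.2.
2. Show Alluzience events with onset after that cut in a separate table.
3. Keep the full-follow-up tables, label them non-comparative, and footnote nominal follow-up of 28 days (powder) and 168 days (Alluzience).
4. Do not substitute events per subject-month.
5. Put the same follow-up footnote on the by-arm concomitant medication and procedure tables (SAP 12.3, 7.4).

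The cost is SAP wording, footnotes (which SAP 14.0 already allows) and a few extra tables. Onset, treatment and visit dates are already collected, so no new data are needed. One limit remains: an Alluzience subject can still report a first-month event at Month 3 or later, so the cut equalises the onset window but not every opportunity to report.

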12.2.1 Overview of Adverse Events

An overview summary table of AEs will be presented by treatment including the number and percentage of subjects reporting an AE for the following categories:

- Subjects reporting at least one AE
- Subjects reporting at least one treatment-related AE
- Subjects reporting at least one serious AE (SAE)
- Subjects reporting at least one treatment-related serious AE (SAE)
- Subjects reporting at least one AE leading to discontinuation of study
- Subjects with AE resulting in death on study

12.2.2 Overview of Treatment-Emergent Adverse Events

A TEAE is an event that emerges during or after treatment, having been absent pre-treatment, or worsens relative to the pre-treatment state.

The number of events and the number and percentage of subjects by treatment with the following categories of TEAEs will be summarized by SOC and PT:

- Subjects reporting at least one TEAE by SOC and PT.
- Subjects reporting at least one TEAE by SOC, PT, and maximum intensity.
- Subjects reporting at least one TEAE by SOC, PT, and relationship (related/not related) to study drug.
- Subjects reporting at least one TEAE leading to discontinuation of study drug dosing by SOC and PT.
- Subjects reporting at least one serious TEAE by SOC and PT.

The number and percentage of subjects who experienced at least one TEAE will be summarized overall and for each SOC and each PT. The percentage will be based on the number of subjects in the safety population. Each subject will contribute at most one count per summarization category. In other words, if a

subject has more than one TEAE with same PT, the subject will be counted only once for that PT. Similarly, if a subject has more than one TEAE for a SOC, the subject will be counted only once in that SOC and PT.

12.2.3 Relationship to Study Drug

A two-point scale (Yes/No) shall be used for the causality assessment. The Investigator shall be asked to indicate a response to each of the following questions in the eCRF:

- "Do you consider that there is a reasonable possibility that the event may have been caused by the study product?"
- "Do you consider that there is a reasonable possibility that the event may have been caused by the study product injection procedure?"

If the answer is "Yes" to either of these questions, the AE is considered related.

Summaries of related AEs (including the total number of events, number and percentage of subjects) will be displayed by treatment group according to the following:

- All AEs related to study product or injection procedure by SOC, PT, and maximum intensity (mild, moderate, or severe)
- All AEs related to study product or injection procedure by SOC, PT, and duration of event
- All AEs related to study product or injection procedure by SOC, PT, and number of days to onset of event
- All AEs by SOC, PT, and action taken (none, medical treatment, non-pharmacological treatment, subject withdrawn)
- All AEs unrelated to study product or injection procedure by SOC, PT, and maximum intensity (mild, moderate, or severe)

If a subject has multiple occurrences of the same SOC or PT, then only the related event will be summarized in the tables for that SOC and PT. Missing relationships will be considered related.

12.2.4 Intensity of the Adverse Event

TEAEs will be summarized by intensity. The intensity of the TEAE is classified into three categories of Mild, Moderate, and Severe. If a subject has multiple occurrences of the same SOC or PT with varying levels of intensity, then the subject will only be counted under the most severe intensity in the table. If the intensity assessment is missing, then an intensity of Severe will be assumed.

12.2.5 Death, Serious Adverse Events, Adverse Events Leading to Discontinuation

A Serious Adverse Event (SAE) is any untoward medical occurrence that

- Results in death,
- Is life threatening,
- Requires in-patient hospitalization or prolongation of existing hospitalization,
- Results in persistent or significant disability/incapacity
- Is a congenital anomaly/birth defect, or
- Important medical events that may not result in death, be life-threatening, or require hospitalization may be considered an SAE when, based upon appropriate medical judgment, they may jeopardize the safety of the subject, and may require medical or surgical intervention to prevent one of the outcomes listed in this definition. Examples of such events are intensive treatment in an emergency room or at home for allergic bronchospasm, blood dyscrasia, or convulsions that do not result in hospitalization.

Table summaries and by-subject listings also will be provided for the following: subject deaths, SAEs, and adverse events leading to study discontinuation.

12.3 Prior and Concomitant Medications and Therapies

Previous therapies are defined as therapies that have been stopped within 4 weeks preceding the screening visit or within timeframes specified in the inclusion/exclusion criteria.

Concomitant therapies are defined as follows:

- Any existing therapies ongoing at the time of the screening visit.
- Any changes to existing therapies (such as changes in dose or formulation) during the course of the clinical study.
- Any new therapies received by the subject since the screening visit.

Drugs, including, but not limited to, prescription, over the counter, birth control pills/patches/hormonal devices, vitamins, herbal medicines/supplements, and homeopathic preparations are to be considered for previous and concomitant therapies

Medications will be included in the concomitant medication summary if they were taken on or after the date of the study drug administration, regardless of when the medication started.

Partial start dates for medications will be imputed via the following rules:

- o Start Date
 - If start date is completely missing, it will be assumed that the medication started at baseline.
 - If the start date is missing the day, the baseline day will be used provided the imputed date is on or after the subject's randomization date; otherwise, the day of randomization will be used.
 - If the start date is missing the month, the randomization month will be used.
 - If the start date is missing the year, the baseline year will be used provided the imputed date is on or after the subject's randomization date; otherwise, the subsequent year after randomization will be used.
- o End Date
 - If end date is completely missing, it will be assumed that the medication is still being taken and will not be imputed.
 - If the end date is missing the day, the last of the month will be used (i.e. UNK-JAN-2022 becomes 31-JAN-2022)
 - If the end date is missing the month, the subsequent month after the start date will be used. If the end date is missing the year, the year of randomization will be used (i.e. 01-JAN-UNK becomes 01-JAN-2022), provided the imputed date is after the start date; otherwise, the subsequent year after start date will be used.

Medications other than study drug will be summarized by the World Health Organization (WHO) Drug Dictionary Anatomical Therapeutic Chemical 3rd level (ATC-3) and preferred name for the FAS population. If the 3rd level term is not available, the next available level (e.g., ATC-2) will be used.

The number and percentage of the subjects who took each medication will be tabulated by treatment, the ATC-3 level and preferred name for concomitant medications. ATC-3 and preferred name will be presented in descending frequency

first, and then alphabetically if there are ties. Each subject will contribute at most one count per summarization category. All concomitant medication data for each subject will be included in the listings. Similar number and percentage of subjects who had concomitant therapies will be tabulated for FAS population by treatment arm. Prior and concomitant medications and therapies will be included in data listings.

